### **7.1.6. SRF617 Postinfusion Medications**

No specific postinfusion medications are required for SRF617.

### **7.1.7. SRF617 Treatment Continuation**

Patients will remain on study treatment until disease progression, unacceptable toxicity, or the completion of approximately 2 years of study treatment. Patients may remain on study treatment longer than 2 years with agreement from the trial Investigator and Sponsor.

## **7.2. Etrumadenant**

### **7.2.1. Etrumadenant Dosage**

Etrumadenant will be taken orally at a daily dose of 150 mg. Enough etrumadenant bottles should be dispensed to cover patient dosing through the next visit. When more than 1 bottle of etrumadenant is dispensed, patients should be instructed to open 1 bottle and consume all contents before opening another bottle. To assess compliance with self-administration of etrumadenant, patients will be required to record the time and date they took each dose in a drug diary; missed doses will also be recorded. Patients will be instructed to bring all unused doses of etrumadenant and their drug diary to the clinic at specified visits for assessments of compliance. See [Table 9](#) for information about possible dose modifications of etrumadenant to manage drug-related toxicities.

### **7.2.2. Etrumadenant Administration**

Etrumadenant must be taken with a full cup or glass of non-carbonated room temperature water. All capsules for the etrumadenant dose should be taken within minutes of each other. Etrumadenant should be taken daily at approximately the same time each day. Patients should only take the prescribed dose of etrumadenant once per day. If the patient forgets to take etrumadenant at the scheduled time, they should take the dose as soon as they remember. However, if the dose is not taken by 9 PM (21:00) that same day, it should be documented as a “missed” dose in the dosing diary and the patient should resume dosing the following day at the planned dose time.

Details about the timing of etrumadenant administration on infusion days are provided in [Table 5](#).

Formulation information for etrumadenant may be found in the etrumadenant Investigator Brochure. Additional information on the administration, distribution, storage, preparation, handling, and destruction of etrumadenant is described in the Pharmacy Manual.

## **7.3. Zimberelimab**

### **7.3.1. Zimberelimab Dosage**

Patients will receive zimberelimab 480 mg IV q4 weeks on Day 1 of a 28-day cycle. Zimberelimab is administered as an IV infusion supplied by the Sponsor.

There will be no dose modifications for zimberelimab in this trial. See [Table 9](#) for additional information about management of drug-related toxicities with zimberelimab.

### **7.3.2. Zimberelimab Administration**

Details about the timing of zimberelimab administration are provided in [Table 5](#).

To reduce the risk of infusion reaction, patients may receive acetaminophen with or without an antihistamine or other standard therapy according to local guidelines as pre-medication prior to an infusion.

Formulation information for zimberelimab may be found in the zimberelimab Investigator Brochure. Additional information on the administration, distribution, storage, preparation, handling, and destruction of zimberelimab is described in the Pharmacy Manual.

## **7.4. Dose Holds, Modifications, and Discontinuations**

Patients will be monitored continuously for toxicity while on study drug. Toxicity severity will be assessed using the NCI-CTCAE version 5.0 or higher. Every effort should be made to administer the study drug according to the planned dose and schedule; however, in the event of significant treatment-related toxicity, administration of study drug may need to be adjusted as described below.

Holding of 1 agent and not the other agents is appropriate if, in the opinion of the Investigator, the toxicity is clearly related to one of the study drugs. Appropriate documentation is required regarding the drug(s) to which the Investigator is attributing the AE. If, in the opinion of the Investigator, the toxicity is related to the combination of all 3 study drugs, then all 3 drugs should be held.

If all 3 drugs have been withheld for > 56 days, then all study treatment should be discontinued.

Patients who discontinue any study drug(s) but are continuing to derive clinical benefit from any of the others may continue treatment at the discretion of the Investigator and Sponsor.

### **7.4.1.1. SRF617**

If in the opinion of the Investigator, the patient experiences any of the toxicities outlined in [Table 6](#) that are not clearly related to disease progression, intercurrent illness, or concomitant medications, then SRF617 dose(s) will be held until recovery of the toxicity to Grade  $\leq 1$  or to the patient's previous Baseline. Appropriate follow-up assessments should be done until adequate recovery occurs as assessed by the Investigator.

**Table 6: Hematologic Toxicities Leading to Dose Hold of SRF617**

| Toxicity   | Recommended Dose Delay or Reduction  |
|--|--|
| Neutropenia   |  |
| Grade 3 (ANC < 1000/ $\mu$ L; $1 \times 10^9/L$ ) with a single temperature of $> 38.3^{\circ}\text{C}$ ( $101^{\circ}\text{F}$ ) or a sustained temperature of $\geq 38^{\circ}\text{C}$ ( $100.4^{\circ}\text{F}$ ) for $> 1$ hour | Hold until toxicity recovers to Baseline and then resume at reduced dose. If Grade $\geq 3$ recurs, permanently discontinue. |
| Grade 4 (ANC < 500/ $\mu$ L; $< 0.5 \times 10^9/L$ ) persisting for $\geq 7$ days, and/or complicated by infection   | Permanently discontinue.   |
| Grade 4 life-threatening consequences; urgent intervention indicated   | Permanently discontinue.   |
| Platelets   |  |
| Grade 3 (platelets $< 50,000-25,000/\mu\text{L}$ ; $< 50.0-25.0 \times 10^9/\text{L}$ ) with associated clinically significant bleeding  | Permanently discontinue.   |
| Grade 4 (platelets $< 25,000/\mu\text{L}$ ; $< 25.0 \times 10^9/\text{L}$ ) of any duration bleeding   | Permanently discontinue.   |
| Anemia  |  |
| Grade 4 anemia defined as life-threatening consequences; urgent intervention indicated (any duration)  | Permanently discontinue.   |
| All other hematologic toxicity  |  |
| Intolerable or recurrent Grade 2   | Hold until resolves to baseline and resume at reduced dose.  |
| Grade 3  | Hold until resolves to baseline and resume at reduced dose.  |
| Recurrent Grade 3 or 4   | Permanently discontinue.   |
| Grade 4 not detailed above   | Permanently discontinue.   |

Abbreviation: ANC = absolute neutrophil count.

Steroids may be used to manage severe (Grade  $\geq 3$ ) hematologic toxicity if thought to be immune-related. All attempts should be made to rule out other causes such as metastases, sepsis, and/or infection. Relevant diagnostic studies such as peripheral blood smear, reticulocyte count, lactate dehydrogenase, haptoglobin, bone marrow biopsy, or Coomb's test, etc., should be considered to confirm the diagnosis. The AE should be reported to the Sponsor regardless of etiology.

In the unlikely event of severe bone marrow suppression, a bone marrow biopsy should be performed, if clinically feasible, to assist in determining causality.

Nonhematologic toxicities that occur during treatment with SRF617 that are not clearly related to disease progression, intercurrent illness, or concomitant medications should be managed according to the guidelines in [Table 7](#).

**Table 7: Nonhematologic Toxicities Leading to Dose Hold, Modification, or Discontinuation of SRF617**

| Toxicity   | Recommended dose delay or reduction   |
|--|---|
| Immune-mediated AEs   |   |
| Grade 2 or Grade 3 immune-mediated AEs   | Hold SRF617 until resolves to Grade $\leq$ 1 and resume with dose reduced by 1 level.   |
| Grade 4 immune-mediated AEs  | Permanently discontinue SRF617.   |
| Hepatotoxicity  |   |
| $> 2 \times$ ULN bilirubin AND Grade $\geq$ 2 ALT/AST ( $> 3 \times$ ULN) in patients who enroll with Grade $\leq$ 1 ALT/AST | In the absence of biliary obstruction or other cause responsible for the concurrent elevation, permanently discontinue SRF617.  |
| OR   |   |
| $> 2 \times$ ULN bilirubin AND doubling of ALT/AST in patients who enroll with Grade 2 ALT/AST                               |   |
| Grade 4 ALT/AST elevation  | Permanently discontinue SRF617.   |
| OR   |   |
| Grade 4 bilirubin elevation  |   |
| Metabolic   |   |
| Grade 3 electrolyte disturbance  | Hold SRF617 until resolves to Grade $\leq$ 1 or Baseline and resume with same dose (first occurrence) or with dose reduced by 1 level after resolution (second occurrence).   |
| Grade 4 electrolyte disturbance  | Hold SRF617 until resolves to Grade $\leq$ 1 or Baseline and resume with same dose if resolves in $\leq$ 72 hours; permanently discontinue if resolution takes $>$ 72 hours.  |
| Gastrointestinal  |   |
| Grade 3 vomiting, diarrhea, or nausea  | Hold SRF617 until resolves to Grade $\leq$ 1 or Baseline and resume with same dose if resolves in $\leq$ 72 hours with supportive care. If it lasts $>$ 72 hours despite optimal supportive care, resume with dose reduced by 1 level.
Patients must be contacted by the Investigator or trial nurse daily until it is clear that the problem has resolved or requires additional support (eg, hospitalization). |
| Grade 4 vomiting or diarrhea   | Permanently discontinue SRF617.   |

| Toxicity  | Recommended dose delay or reduction  |
|---|--|
| Other nonhematologic toxicities  |  |
| Grade 2 or Grade 3 AEs that, in the opinion of the Investigator, require dose reduction   | Hold SRF617 until resolves to Grade $\leq$ 1 or Baseline and resume with dose reduced by 1 level.
Evaluate at least once weekly after the initial identification of the toxicity until its resolution or stabilization. |
| Grade 4 a AEs that, in the opinion of the Investigator, require dose reduction | Permanently discontinue SRF617.  |
| Other  |  |
| Treatment delays of $>$ 56 days due to drug-related toxicities                            | Permanently discontinue SRF617.  |

Abbreviations: AE = adverse event; ALT = alanine aminotransferase; AST = aspartate aminotransferase; ULN = upper limit of normal.

a Other than laboratory abnormalities that Investigator deems clinically insignificant and that last  $\leq$  72 hours.

For toxicities that also meet the stopping rule criteria for safety (see Section 4.6), after the first occurrence of the toxicity, the Investigator may resume SRF617 treatment at 1 dose level lower upon recovery of the toxicity to Grade  $\leq$  1 or Baseline value (Table 8). For toxicities that do not meet the stopping rule criteria for safety, the Investigator may resume SRF617 treatment at the same dose level upon recovery of the toxicity to Grade  $\leq$  1 or Baseline value. Any patient who requires more than 2 dose level reductions or requires holding of SRF617 for more than 56 days will be permanently discontinued from the study drug.

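### The paragraph after Table 7 sets the SRF617 resumption dose by stopping-rule status, without excepting the toxicities for which Table 7 calls for a reduction or permanent discontinuation

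*Protocol*

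**What the plan says.** The lead-in to Table 7 (Protocol Section 7.4.1.1) says that nonhematologic toxicities not clearly due to progression, intercurrent illness or other medication "should be managed according to the guidelines in" Table 7. In that table, "Grade 2 or Grade 3 immune-mediated AEs" lead to a hold and then a one-level reduction, and "Grade 4 immune-mediated AEs" lead to permanent discontinuation. Grade 4 vomiting or diarrhea, and Grade 4 ALT/AST or bilirubin, also end SRF617 permanently.

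The paragraph after the table uses another test. If the toxicity also meets Section 4.6, then after a first occurrence "the Investigator may resume SRF617 treatment at 1 dose level lower upon recovery of the toxicity". If not: "For toxicities that do not meet the stopping rule criteria for safety, the Investigator may resume SRF617 treatment at the same dose level". Both routes require recovery to Grade 1 or lower, or to Baseline. One further limit follows: "Any patient who requires more than 2 dose level reductions or requires holding of SRF617 for more than 56 days" must stop the drug permanently.

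Section 4.6 has three limbs: a related Grade 3 or higher event not excepted by Table 4, a treatment-related toxicity that ends treatment in Cycle 1, and a delay of more than 14 days in starting Cycle 2 because of toxicity. Table 4 excepts, among others, nausea, vomiting and diarrhea of Grade 3 or higher that respond to supportive care within 3 days, and treatable or reversible nonhematologic laboratory abnormalities.

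**The concern.** Table 4 was written to decide whether the trial is halted for committee review. Through the paragraph after Table 7 it also helps to set the dose at which an individual patient restarts SRF617. Those are different questions. An event may be unremarkable as a trial-level signal and still be a reason to reduce or stop the drug in the patient who had it. Where the two texts differ, an Investigator can cite the protocol for either course, and the paragraph gives the more permissive one. What is at stake is the dose a patient receives after a toxicity, up to full dose after an event for which Table 7 ends SRF617.

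**Working it through.** The plan gives no figure to reproduce here. The check is a row-by-row comparison, with doses from Table 8.

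**Does Section 4.6 apply to one patient?** As written it counts 2 or more of the 6 lead-in patients. However, Table 2 footnote f and Table 3 footnote a call for an extra SRF617 sample when a single patient has a toxicity meeting the stopping rules, including outside Cycle 1. The paragraph after Table 7 uses the criteria in the same way. I therefore read them per patient, and every comparison below rests on that reading.

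**Dose per 28-day cycle, two infusions, starting from 1400 mg**
- Same dose: 1400 × 2 = 2800 mg
- One level lower: 700 × 2 = 1400 mg
- Discontinued: 0 mg

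**Conflicts on the face of the text**

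| Event | Section 4.6 status | Paragraph | Table 7 | mg/cycle |
|---|---|---|---|---|
| Grade 2 immune-mediated AE | Meets no limb | Same dose | One level lower | 2800 vs 1400 |
| Related Grade 4 immune-mediated AE | Met | One level lower | Discontinue | 1400 vs 0 |
| Grade 4 vomiting or diarrhea responding within 3 days | Excepted by Table 4, no other limb met | Same dose | Discontinue | 2800 vs 0 |

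The third row needs a qualification. If Table 7 is followed for a related Grade 4 event in Cycle 1, treatment stops, which arguably meets the limb on discontinuation in Cycle 1. The same-dose sentence would then not apply. So 2800 versus 0 arises mainly after Cycle 1, or when the event is judged unrelated.

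**Conflicts that depend on the course of the event or on how Table 4 is read**

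| Event | Condition | Paragraph | Table 7 | mg/cycle |
|---|---|---|---|---|
| Grade 3 nausea, vomiting or diarrhea | Responds within 3 days, takes over 72 hours to resolve | Same dose | One level lower | 2800 vs 1400 |
| Grade 4 ALT/AST or bilirubin | Table 4 laboratory row applies | Same dose | Discontinue | 2800 vs 0 |
| Second Grade 3 electrolyte disturbance | Table 4 laboratory row applies | Same dose | One level lower | 2800 vs 1400 |

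The Grade 3 gastrointestinal row turns on one word. Table 4 asks that the event *respond* within 3 days. Table 7 asks that it *resolve* to Grade 1 or lower, or to Baseline, within 72 hours. Diarrhea that improves to Grade 2 on day 3 and resolves on day 6 passes the first test and fails the second.

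**Was reduction after a Grade 4 event intended?** Table 7 has five Grade 4 entries:
- Three discontinue outright: immune-mediated; ALT/AST or bilirubin; vomiting or diarrhea.
- One covers other nonhematologic "AEs that, in the opinion of the Investigator, require dose reduction" and discontinues those, with a footnote: "Other than laboratory abnormalities that Investigator deems clinically insignificant and that last" no more than 72 hours.
- One, electrolytes, gives the same dose or discontinuation according to resolution within 72 hours.

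That is 3 + 1 + 1 = 5, and none prescribes a reduction. Yet the text after Table 8 bars re-escalation for patients reduced because of a Grade 4 nonhematologic event. Someone therefore contemplated such reductions, and the paragraph after Table 7 is a route to them.

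**Reach beyond Table 7.** The paragraph speaks of toxicities without restriction, so it can also be read onto the hematologic rules in Table 6 and onto infusion reactions. For infusion reactions the protocol recommends no SRF617 dose reduction and sets its own discontinuation rules.

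**The case against.** The best reply is that the texts can be read together. Table 7 is the stated management guide, and a drug it has permanently discontinued has no resumption step. The paragraph says only that the Investigator *may* resume, and its word *also* can be read as adding a condition to Table 7. The table's own column is headed as a recommendation. Section 7.1.2 leaves reduction and discontinuation to clinical judgment, and Section 4.7 allows discontinuation when medically necessary. For related Grade 4 gastrointestinal events, Table 10 stops etrumadenant and zimberelimab, which points the same way as Table 7.

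Much of this stands. It means that the stricter course is always open, and that the discontinuation conflicts are partly a matter of reading. It does not remove the point. No sentence gives Table 7 precedence, and Section 4.5 refers generally to Section 7.4, which contains both texts. For a Grade 2 immune-mediated event the discontinuation argument is unavailable: both texts resume the drug, at different doses.

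A reader might infer that the protocol directs full-dose SRF617 after Grade 4 toxicity. It does not; it permits resumption. A reader might also infer that patients were re-dosed against Table 7. The documents give no counts of these events and no record of how any was handled.

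**Conclusion.** The conflict is real but limited. Three kinds of event receive different instructions on the face of the text, with differences of 1400, 1400 and 2800 mg per cycle. Three more can do so: Grade 3 gastrointestinal events by their time course, and the two laboratory cases only if Table 4's wording on reversible abnormalities covers them. All of this assumes that Section 4.6 is read per patient and that the patient was receiving 1400 mg per dose. These are dose differences, not estimates of risk.

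Practical reach is small. SAP Section 2 reports 15 patients treated as of 19 June 2023, with no further enrollment, so at most 15 could be affected as of that date. Those already enrolled or consented could continue treatment under the protocol, so the text still mattered for them. The documents do not say how many remained on treatment. A reader might look for an effect on the trial's conclusions, but no alpha, power or planned analysis depends on this paragraph.

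**What to change.** Begin the paragraph after Table 7 with: *Unless Table 6, Table 7 or the infusion-related reaction guidance specifies the resumption dose or permanent discontinuation, ...*

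Add: *The Table 4 exceptions apply only to the trial stopping rule and do not override Tables 6 and 7.*

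Leave unchanged the Investigator's discretion in Section 7.1.2 and the bar on re-escalation in the text after Table 8. The cost is one clause and one sentence in a protocol clarification, with no new data, visits or analysis.

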**Table 8: Recommended Dose Reductions for SRF617**

|        | Initial dose | First dose reduction | Second dose reduction |
|--------|--------------|----------------------|-----------------------|
| SRF617 | 1400 mg      | 700 mg               | 350 mg                |

Patients who have a dose reduction because of a toxicity may be eligible for a dose increase back to the dose level before the reduction if the following criteria are met and approved by the Sponsor:

- Patient has tolerated the lower dose level for  $>$  1 treatment cycle
- Patient has recovered to Baseline levels from the toxicity that caused the dose reduction

Patients who have a dose reduction because of a Grade 4 nonhematologic AE may not re-escalate the dose after a dose reduction.

### *Infusion-Related Reactions*

For infusion reactions of any grade/severity, immediately interrupt the SRF617 infusion and manage symptoms. Management of infusion reactions may require reduction in the rate of infusion or treatment discontinuation of SRF617, as outlined below:

- Grade 1 to 2 (mild or moderate): Once reaction symptoms resolve, resume the infusion at no more than half the rate at which the reaction occurred. If the patient does not experience any further reaction symptoms, infusion rate escalation may resume in increments and at intervals clinically appropriate up to the maximum rate of 100 mL/h.
- Grade 3 (severe): Once reaction symptoms resolve, consider restarting the infusion at no more than half the rate at which the reaction occurred. Repeat the procedure above in the event of recurrence of Grade 3 symptoms. Permanently discontinue SRF617 upon the third occurrence of a Grade 3 or greater infusion reaction.
- Grade 4 (life-threatening): Permanently discontinue SRF617 treatment.

No dose reductions of SRF617 for infusion-related reactions are recommended.

For any patient who has a Grade  $\geq 2$  infusion reaction with SRF617, steroid premedication should be used for all subsequent infusions (see Section [7.1.5](#)).

#### **7.4.1.2. Etrumadenant and Zimberelimab**

Dose holds of etrumadenant or zimberelimab are allowed throughout the trial for no more than 56 days. If either drug has been withheld for more than 56 days, then that drug should be permanently discontinued.

For management of drug-related toxicities, the dose of etrumadenant may be reduced up to 2 times as outlined in [Table 9](#). If further dose reduction below 75 mg is indicated, etrumadenant should be discontinued. After dose reduction, the dose may be escalated during subsequent administrations at the Investigator's discretion with Medical Monitor approval. There will be no dose reductions for zimberelimab in this trial.

**Table 9: Recommended Dose Reductions for Etrumadenant**

|              | Initial dose | First dose reduction | Second dose reduction |
|--------------|---------------------|-----------------------------|------------------------------|
| Etrumadenant | 150 mg              | 100 mg                      | 75 mg                        |
| Zimberelimab | 480 mg              | N/A                         | N/A                          |

Guidelines for the management of patients who experience specific AEs are provided in [Table 10](#). For AEs for which management guidelines are not provided, patients should be managed, and study treatment should be modified as deemed appropriate by the Investigator according to best medical practice.

**Table 10: Guidelines for Management of Patients who Experience Adverse Events Considered to be Related to Etrumadenant and/or Zimberelimab**

| Event   | Severity         | Etrumadenant action to be taken   | Zimberelimab action to be taken  |
|---|------------------|---|--|
| Infusion-related reaction
(including hypersensitivity and anaphylaxis)                      | Grade 1-2 | Continue etrumadenant at the same dose level. Institute symptom-directed supportive care according to institutional guidelines.   | Refer to the NCCN or institutional guidelines for the Management of Immune CPI-Related Toxicities for symptom-directed supportive care. Zimberelimab, if interrupted, may be withheld for up to 56 days after event onset.                 |
|   | Grade 3-4 | Consider etrumadenant dose modification as clinically indicated, otherwise continue at the same dose.

Institute symptom-directed supportive care according to institutional guidelines.  | Consider zimberelimab treatment interruption or permanent discontinuation as clinically indicated. Refer to the NCCN or institutional guidelines for the Management of Immune CPI Related Toxicities for symptom-directed supportive care. |
| Dermatologic toxicity
(including but not limited to rash, maculopapular rash, and pruritis) | Grade 1   | Continue etrumadenant at the same dose level. Immediately institute supportive care measures for symptomatic relief.  | Refer to the NCCN or institutional guidelines for the Management of Immune CPI-Related Toxicities for symptom-directed supportive care. Zimberelimab, if interrupted, may be withheld for up to 56 days after event onset.                 |
|   | Grade 2   | Consider etrumadenant dose modification as clinically indicated; otherwise continue at the same dose.

For suspected etrumadenant-related events: 
 
Immediately institute supportive measures.
 
If the event does not resolve to Grade 1 or better within 7 days, consider dose interruption. If event resolves to Grade 1 or better, resume etrumadenant at the same dose or with a one-level dose reduction (Table 9).
 
Etrumadenant dose re-escalation is permitted at the Investigator's discretion.
 
 |  |
|   | Grade 3   | Withhold etrumadenant for at least 7 days until toxicity resolves to Grade 1 or better.

For suspected etrumadenant-related events: 
 
Immediately institute supportive measures.
 
If event resolves to Grade 1 or better within 56 days, resume etrumadenant with a one-level dose reduction (Table 9).a If not, permanently discontinue etrumadenant and contact Medical Monitor.
 
  |  |

| Event   | Severity  | Etrumadenant action to be taken  | Zimberelimab action to be taken  |
|---|---|--|--|
|   |   | 
 
Etrumadenant dose re-escalation is permitted at the Investigator's discretion.
 
   |  |
|   | Grade 4  | Permanently discontinue etrumadenant and contact Medical Monitor   | Permanently discontinue zimberelimab and contact Medical Monitor   |
| Hepatic toxicity
(including elevations in transaminases and/or bilirubin) | Grade 1-2
ALT/AST $\leq 5 \times$ ULN                     | Continue etrumadenant at the same dose level at the Investigator's discretion. Monitor LFTs more frequently until return to $< 3 \times$ ULN or Baseline.  | Refer to the NCCN or institutional guidelines for the Management of Immune CPI-Related Toxicities for symptom-directed supportive care. Zimberelimab, if interrupted, may be withheld for up to 56 days after event onset. |
|   | Grade 3
ALT/AST $> 5 \times$ ULN but $\leq 20 \times$ ULN | 
For suspected non-immune-mediated transaminase elevations:
 
 
Withhold etrumadenant and zimberelimab for up to 56 days.
 
Monitor LFTs at least weekly for a minimum of 4 weeks until transaminases return to <math>< 3 \times</math> ULN or Baseline.
 
Consider patient referral to GI specialist for evaluation and liver biopsy to establish etiology of hepatic injury.
 
If event resolves to Grade 1 or better within 56 days, resume etrumadenant with a one-level dose reduction (Table 9) and resume zimberelimab.a If not, permanently discontinue etrumadenant and zimberelimab and contact Medical Monitor.
 
 
For suspected immune-mediated transaminase elevations:
 
 
Permanently discontinue zimberelimab and contact Medical Monitor.
 
Withhold etrumadenant for up to 56 days.
 
Consider patient referral to GI specialist for evaluation and liver biopsy to establish etiology of hepatic injury.
 
Initiate treatment with corticosteroids equivalent to 1-2 mg/kg/day oral prednisone. If event does not improve within 48 hours after initiating corticosteroids, consider adding an immunosuppressive agent.
 
If event resolves to Grade 1 or better within 56 days, taper corticosteroids over <math>\geq 1</math> month and resume etrumadenant with a one-level dose reduction (Table 9).a If not, permanently discontinue etrumadenant and contact Medical Monitor.
 
 |  |
|   | Grade 4
ALT/AST $> 20 \times$ ULN                         | Permanently discontinue etrumadenant and contact Medical Monitor. For suspected immune-mediated transaminase elevations, follow Grade 3 management guidelines.   | Permanently discontinue zimberelimab and contact Medical Monitor. For suspected immune-mediated transaminase elevations, follow Grade 3 management guidelines.   |
|   | ALT/AST $> 3 \times$ ULN with                                       | 
 
Permanently discontinue etrumadenant and zimberelimab and contact Medical Monitor.
 
Monitor liver function at least weekly until values return to Baseline.
 
  |  |

| Event  | Severity                       | Etrumadenant action to be taken   | Zimberelimab action to be taken  |
|--|--------------------------------|---|--|
|  | concurrent bilirubin > 2 × ULN | 
 
Investigate causes for elevated bilirubin and initiate treatment according to institutional guidelines.
 
Exception: Patients with Gilbert syndrome who develop elevated transaminases should be managed as per the above outlined recommendations for the respective observed elevation of ALT and/or AST.
 
   |  |
| Fatigue  | Grade 1-2                      | Continue etrumadenant at the same dose level. Institute symptom-directed supportive care according to institutional guidelines.   | Refer to the NCCN or institutional guidelines for the Management of Immune CPI-Related Toxicities for symptom-directed supportive care. Zimberelimab, if interrupted, may be withheld for up to 56 days after event onset.                 |
|  | Grade 3-4                      | 
Consider etrumadenant dose modification as clinically indicated, otherwise continue at the same dose.a
 
Institute symptom-directed supportive care according to institutional guidelines.
   | Consider zimberelimab treatment interruption or permanent discontinuation as clinically indicated. Refer to the NCCN or institutional guidelines for the Management of Immune CPI Related Toxicities for symptom-directed supportive care. |
| Gastrointestinal toxicity
(including but not limited to diarrhea and colitis) | Grade 1                        | 
 
Continue etrumadenant at the same dose level.
 
Initiate symptomatic treatment and monitor closely.
 
Endoscopy is recommended if symptoms persist > 7 days.
 
   | Refer to the NCCN or institutional guidelines for the Management of Immune CPI-Related Toxicities for symptom-directed supportive care. Zimberelimab, if interrupted, may be withheld for up to 56 days after event onset.                 |
|  | Grade 2                        | 
 
Consider etrumadenant dose modification as clinically indicated, otherwise continue at the same dose.
 
Initiate symptomatic treatment.
 
Referral to GI specialist is recommended.
 
For recurrent events or events that persist > 5 days, initiate treatment with corticosteroids equivalent to 1-2 mg/kg/day oral prednisone.
 
1st occurrence: If etrumadenant was withheld and event resolves to Grade 1 or better within 56 days, resume etrumadenant at the same dose level.
 
Recurrent or persistent events: If etrumadenant was withheld and event resolves to Grade 1 or better within 56 days, resume etrumadenant with a one-level dose reduction (Table 9).a If not, permanently discontinue etrumadenant and contact Medical Monitor.
 
 |  |

| Event  | Severity         | Etrumadenant action to be taken   | Zimberelimab action to be taken                         |
|--|------------------|---|---|
|  |                  | 
 
Etrumadenant dose re-escalation is permitted at the Investigator's discretion.
 
  |   |
|  | Grade 3   | 
Withhold etrumadenant for up to 56 days after event onset.
 
For suspected immune-mediated events (including colitis):
 
 
Refer patient to GI specialist for evaluation and confirmatory biopsy.
 
Initiate treatment with corticosteroids equivalent to 1-2 mg/kg/day IV methylprednisolone and convert to 1-2 mg/kg/day oral prednisone or equivalent upon improvement.
 
Follow guidance for Grade 2 recurrent or persistent events.
 
   |   |
|  | Grade 4   | 
Permanently discontinue etrumadenant and zimberelimab and contact Medical Monitor.
 
 
Refer patient to GI specialist for evaluation and confirmation biopsy.
 
Initiate treatment with corticosteroids equivalent to 1-2 mg/kg/day IV methylprednisolone and convert to 1-2 mg/kg/day oral prednisone or equivalent upon improvement. If event does not improve within 48 hours after initiating corticosteroids, consider adding an immunosuppressive agent.
 
If event resolves to Grade 1 or better, taper corticosteroids over <math>\geq</math> 1 month.
 
 |   |
| Etrumadenant-related toxicities not described above | Grade 1-2 | Consider etrumadenant dose modification as clinically indicated, otherwise continue at the same dose. Institute symptom directed supportive care according to institutional guidelines.   | Continue zimberelimab.                                  |
|  | Grade 3   | 
 
Withhold etrumadenant for up to 56 days after event onset.
 
If event resolves to Grade 1 or better within 56 days resume etrumadenant with a one level dose reduction.a If not, permanently discontinue etrumadenant and contact Medical Monitor.
 
Etrumadenant dose re-escalation is permitted at the Investigator's discretion.
 
  | Continue zimberelimab at the Investigator's discretion. |

| Event  | Severity         | Etrumadenant action to be taken   | Zimberelimab action to be taken  |
|--|------------------|---|--|
|  | Grade 4   | Permanently discontinue etrumadenant and contact Medical Monitor.   | Withhold zimberelimab for up to 56 days after event onset. If event improves and Medical Monitor agrees that zimberelimab should be continued, resume zimberelimab; otherwise, permanently discontinue zimberelimab.       |
| Zimberelimab-related toxicities not described above | Grade 1-2 | Continue etrumadenant at the same dose level.   | Refer to the NCCN or institutional guidelines for the Management of Immune CPI-Related Toxicities for symptom-directed supportive care. Zimberelimab, if interrupted, may be withheld for up to 56 days after event onset. |
|  | Grade 3   | 
 
Consider etrumadenant dose modification as clinically indicated, otherwise continue at the same dose.
 
Initiate symptomatic treatment.
 
If etrumadenant was withheld and event resolves to Grade 1 or better within 56 days, resume etrumadenant with a one-level dose reduction.a
 
Etrumadenant dose re-escalation is permitted at the Investigator's discretion.
 
 | Refer to the NCCN or institutional guidelines for the Management of Immune CPI-Related Toxicities for symptom-directed supportive care. Zimberelimab, if interrupted, may be withheld for up to 56 days after event onset. |
|  | Grade 4   | Permanently discontinue etrumadenant and contact Medical Monitor.   | Permanently discontinue zimberelimab and contact Medical Monitor.  |

Abbreviations: ALT = alanine aminotransferase; AST = aspartate aminotransferase; CPI = checkpoint inhibitor; GI = gastrointestinal; IV = intravenous; LFT = liver function test; NCCN = National Comprehensive Cancer Network; ULN = upper limit of normal

a The dose of etrumadenant can be reduced from 150 mg to 100 mg (ie, one dose level) and then from 100 mg to 75 mg for management of drug-related toxicities. Additional dose reductions are not allowed. If a dose reduction is indicated for a patient receiving the 75 mg dose of etrumadenant, then that patient should discontinue etrumadenant.

